(*) Bestall J.C. et al. Thorax. 1999 Jul;54(7):581-6. Usefulness of the Medical Research Council (MRC) dyspnoea scale as a measure of disability in patients with chronic obstructive pulmonary disease.

From the *Global Strategy for the Diagnosis, Management and Prevention of COPD*, Global Initiative for Chronic Obstructive Lung Disease (GOLD) 2016. Available from: <http://www.goldcopd.org/>. (accessed on March 2016).

3. Patient Satisfaction Questionnaire

Please choose the number which best describes your satisfaction with Spiolto® Respimat®.

What is your overall satisfaction with the Spiolto® Respimat® treatment?

1 very unsatisfied 	2 unsatisfied 	3 rather unsatisfied 	4 neither satisfied nor unsatisfied 	5 rather satisfied 	6 satisfied 	7 very satisfied 
---	--	---	---	---	--	---

How satisfied are you with inhaling from the Respimat® device?

1 very unsatisfied 	2 unsatisfied 	3 rather unsatisfied 	4 neither satisfied nor unsatisfied 	5 rather satisfied 	6 satisfied 	7 very satisfied 
---	--	---	---	---	--	---

How satisfied are you with the handling of the Respimat® inhalation device?

1 very unsatisfied 	2 unsatisfied 	3 rather unsatisfied 	4 neither satisfied nor unsatisfied 	5 rather satisfied 	6 satisfied 	7 very satisfied 
---	--	---	---	---	--	---

4. Physicians' Global Evaluation (PGE) to be used directly within the eCRF

General condition of the patient at the initial examination (Visit 1)

Please mark with a cross as applicable

Poor
 1 2

Satisfactory
 3 4

Good
 5 6

Excellent
 7 8

General condition of the patient after approximately 6 weeks of treatment (Visit 2)

Please mark with a cross as applicable

Poor
 1 2

Satisfactory
 3 4

Good
 5 6

Excellent
 7 8

APPROVAL / SIGNATURE PAGE

Document Number: c10705101

Technical Version Number: 1.0

Document Name: clinical-trial-protocol-version-1.0

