5.2.4. Analysis of secondary endpoints

The secondary endpoints are listed below:

- Changes in PF-10 score from visit 1 to visit 2
- Patient's general condition assessed by the physician (PGE score) at visit 1 and visit 2.
- Patient satisfaction with Spiolto® Respimat® at visit 2.

The head physician will use the Physician's Global Evaluation (PGE) to assess the patient's general condition on an 8-point ordinal scale from 1 (very poor) to 8 (excellent). The PGE will be completed before and approximately 6 weeks after the start of treatment.

A patient **satisfaction** questionnaire will also be completed during visit 2, using a 7-point ordinal scale, from 1 (very unsatisfied) to 7 (very satisfied).

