5.2.7. Statistical methodology

In this observational study, cross-sectional data will be collected at the start of the study and longitudinal follow-up data will be collected in the 6-week period for patients with COPD disease requiring dual bronchodilator therapy in routine clinical practice.

Baseline data will be described using a cross-sectional approach. Longitudinal follow-up data will be summarised descriptively. Due to the observational nature of this study, it is not planned to carry out (confirmatory) hypothesis testing in a strict statistical sense. Analyses are descriptive in nature and confidence intervals and p-values from statistical models will be used for exploratory purposes. No adjustments for multiple testing will be carried out in the statistical significance evaluation. Consequently, significant differences may be observed by chance along and p-values should be interpreted as exploratory and treated with caution. No formal hypothesis testing will be performed as this is a self-controlled study.

The statistical characteristics presented in the results tables will include: N (total number of valid values), mean, standard deviation (SD), 95% confidence interval of the mean (95% CI), median, 25th and 75th percentiles (P25 and P75, respectively), minimum and maximum (min and max, respectively) for continuous endpoints. The categorical endpoints will be described by their absolute and relative frequencies. The proportion rates and the 95% CIs will be provided when appropriate.

For the primary endpoint, the proportion of patients with therapeutic success at visit 2 (a 10-point increase in the PF-10 score between visit 1 and visit 2) together with the 95% confidence interval will be presented.

For the secondary endpoints:

- Changes in PF-10 score from visit 1 to visit 2
- Patient's general condition assessed by the physician (PGE score) at visit 1 and visit 2.
- Patient satisfaction with Spiolto® Respimat® at visit 2.

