The patient's general condition (PGE score) at visit 1 and visit 2, the mMRC at visit 1 and patient satisfaction at visit 2 are categorical endpoints, so they will be analysed in frequency tables. The change from visit 1 to visit 2 in the PF-10 score is a continuous assessment criterion, so it will be analysed by: n (total number of valid values), mean, standard deviation (SD), 95% confidence interval of the mean (95% CI), median, 25th and 75th percentiles (P25 and P75, respectively), minimum and maximum (min and max, respectively).

Changes in the PF-10 between visit 1 and visit 2 will be analysed using a paired t-test or the non-parametric Wilcoxon Rank-Sum Test for data with non-normal distribution). Changes in the PGE between visit 1 and visit 2 will be analysed using McNemar test.

Data on safety will be reported according to local requirements. Statistical analyses and reporting of adverse reactions (ARs)/adverse events (AEs) will be descriptive in nature. The incidences of ARs and AEs will be analysed in relation to the number of treated patients.

Every effort will be made to collect complete data at the specified study visits (see DMP). Any data removed from the analysis will be documented, recording the site and the patient number, as well as the reason for the removal (see the ANNEX 1. DB DEBUGGING).

A statistical significance level of 0.05 will be applied in all the statistical tests. The evaluation will be carried out using SAS® software, version 9.4 or later.

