6.4.2. Analysis of secondary endpoints

This section will describe the data corresponding to the secondary efficacy endpoints.

Changes in PF-10 score

A descriptive analysis of the PF-10 score from the baseline visit (visit 1) to the visit after 6 weeks (visit 2), as well as the change (difference visit 2 - visit 1), will be conducted in this section.

Table 22. PF-10 score at baseline visit, after 6 weeks and change – Full Analysis Set (FAS)									
	n	mean	SD	(95% CI)	Median	[P25-P75]	Min	Max	P¹
Baseline PF-10									-
(Visit 1)									-
PF-10 after 6 weeks (Visit 2)									-
Change in PF-10 (v2-v1)									

¹ paired t-test /Wilcoxon Rank-Sum

Figure 5. PF-10 Score – Full Analysis Set (FAS)

[line/bar charts of the mean/median PF-10 at the baseline visit (visit 1) and the visit after 6 weeks (visit 2)]

Table 23. Change in PF-10 score according to therapeutic success – Full Analysis Set (FAS)

	n	mean	SD	(95% CI)	Median	[P25-P75]	Min	Max	P ¹
Baseline PF-10 (visit 1)									
Therapeutically successful									
Not therapeutically successful									
PF-10 after 6 weeks (visit 2)									
Therapeutically successful									
Not therapeutically successful									
Change in PF-10 (v2-v1)									
Therapeutically successful									
Not therapeutically successful									

¹ independent two-sample t-test/Mann–Whitney U test

Figure 6. PF-10 score according to therapeutic success – Full Analysis Set (FAS)

[line/bar charts of the mean/median PF-10 at the baseline visit (visit 1) and the visit after 6 weeks (visit 2)]

according to therapeutic success]

Patient's general condition - PGE score

A descriptive analysis of the PGE score at the baseline visit (visit 1) and the visit after 6 weeks (visit 2) will be conducted in this section, to assess the patient's general condition according to the investigator, using an 8-point ordinal scale from 1 (very poor) to 8 (excellent).

Table 24. General condition of the patient – PGE score as assessed by the physician at the baseline visit and after 6 weeks in completed patients – Full Analysis Set (FAS)

	Baseline (Visit 1)	6 weeks (Visit 2)	P ¹
PGE score n (%)			
1			
2			

Table 24. General condition of the patient – PGE score as assessed by the physician at the baseline visit and after 6 weeks in completed patients – Full Analysis Set (FAS)

	Baseline (Visit 1)	6 weeks (Visit 2)	P ¹
3			
4			
5			
6			
7			
8			
Pooled PGE Score n (%)			
Poor (1-2)			
Satisfactory (3-4)			
Good (5-6)			
Excellent (7-8)			

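### McNemar's test is named for the change in PGE, but the PGE has 8 ordered scores or 4 pooled categories, so the Table 24 p-value is underspecified

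*SAP*

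**What the plan says.** **The test.** SAP 5.2.7 (Statistical methodology) says: "Changes in the PGE between visit 1 and visit 2 will be analysed using McNemar test". The footnote to the P column of Table 24 (SAP 6.4.2) repeats the name and adds nothing.

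**The scale.** SAP 5.2.4 has the physician rate the patient's "general condition on an 8-point ordinal scale from 1 (very poor) to 8 (excellent"). Protocol 9.4 describes the same scale. The rating form in Protocol Annex 3, item 4, places scores 1 to 8 under four labels at each visit; its second half is headed "General condition of the patient after approximately 6 weeks of treatment (Visit 2"). Table 24 lists the eight scores, then a block headed "Pooled PGE Score n" (%) with Poor (1-2), Satisfactory (3-4), Good (5-6) and Excellent (7-8).

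**Status of the analysis.** SAP 5.2.7 says that the PGE, mMRC and satisfaction scores "are categorical endpoints, so they will be analysed in frequency tables". It also says that "p-values should be interpreted as exploratory and treated with caution", and then that "A statistical significance level of 0.05 will be applied in all the statistical tests". The protocol names no test for the PGE.

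**The concern.** McNemar's test uses the two discordant counts of a paired two-by-two table. For a scale with more than two levels, someone must choose a split or replace the test with an extension. The SAP does neither, and the possible readings test different hypotheses. A split asks whether more patients crossed one boundary upwards than downwards. Bowker's test asks whether the whole square table is symmetric; it ignores the order of the categories and is not aimed at net improvement. Row-by-row tests ask whether the share in each category changed.

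The PGE is one of three named secondary endpoints. Table 24 otherwise shows only the distributions at the two visits, so the p-value is its only result that uses each patient's own change. If the choice is made after the data are seen, whether the change is reported as significant could depend on it.

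**Working it through.** **1. The plan's own figures.** The documents give no figure for the PGE test, so there is none to reproduce. The only sizing figure concerns the primary endpoint: 0.50 ± 1.96·√(0.25/900) = 46.7% to 53.3%, and 900/0.90 = 1000, both as stated. It is used here only as the source of n = 900.

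**2. The open choices.**
- Cut-points: 8 − 1 = 7 on the scores, of which 4 − 1 = 3 are boundaries of the pooled categories (3 or more, 5 or more, 7 or more).
- Bowker's test has k(k−1)/2 degrees of freedom: 8·7/2 = 28 for the 8x8 table, 4·3/2 = 6 for the 4x4 table.
- Row by row: 8 + 4 = 12 tests.

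**3. One invented table (n = 900, not study data).** Rows are visit 1, columns visit 2.

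| | Poor | Satisf. | Good | Excellent |
|---|---|---|---|---|
| Poor | 60 | 40 | 5 | 0 |
| Satisf. | 32 | 300 | 60 | 4 |
| Good | 5 | 62 | 230 | 20 |
| Excellent | 0 | 6 | 40 | 36 |

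McNemar is (b − c)²/(b + c) on 1 df, with b patients crossing upwards and c downwards:
- Poor versus the rest: (45 − 37)²/82 = 0.78, p = 0.377.
- Poor or Satisfactory versus Good or Excellent: (69 − 73)²/142 = 0.11, p = 0.737.
- Excellent versus the rest: (24 − 46)²/70 = 6.91, p = 0.009.

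Bowker sums the same form over pairs of cells: 64/72 + 0/10 + 4/122 + 4/10 + 400/60 = 7.99. One pair is empty, leaving 5 df and p = 0.157. Stuart-Maxwell (marginal homogeneity) gives 7.72 on 3 df, p = 0.052. The signed-rank test gives p = 0.325. The same data thus fall on either side of 0.05 depending on the reading.

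**4. Simulation.** All PGE inputs are assumptions. Scores are bivariate normal with correlation 0.6, SD 1.2 or 1.5, visit 1 mean 4.0 or 4.5 and a mean shift at visit 2, rounded and limited to 1–8. Each setting has n = 900 and 1500 trials, so the simulation error is at most 1.96·√(0.25/1500) = 2.5 points. The signed-rank test drops zero differences, Bowker drops empty pairs from its df, and McNemar has no continuity correction.

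| | Shift 0.15 | Shift 0.25 |
|---|---|---|
| Signed-rank, power | 89–97% | about 100% |
| Bowker 8x8, power | 34–59% | 91–99% |
| Bowker 4x4, power | 53–72% | 97% or more |
| McNemar, three pooled boundaries, power | 19–78% | 45–99% |
| The three boundaries disagree at 0.05 | 71–84% of trials | 56–62% of trials |

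McNemar power at a shift of 0.15, by boundary:

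| SD, visit 1 mean | 3 or more | 5 or more | 7 or more |
|---|---|---|---|
| 1.2, 4.0 | 46% | 75% | 19% |
| 1.2, 4.5 | 28% | 78% | 34% |
| 1.5, 4.0 | 40% | 57% | 20% |
| 1.5, 4.5 | 28% | 61% | 33% |

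If Bowker 8x8 keeps its nominal 28 df despite empty pairs, its power at 0.15 falls to 11–16%. At a shift of 0.50 the three boundaries disagree in only 1–2% of trials. With no true change, at least one of the 12 row-by-row tests falls below 0.05 in 35–37% of trials.

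**The case against.** Five points can be made for the plan.

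- **The endpoint is the PGE at each visit, not its change**, and the frequency tables deliver that in full. This is true, and it limits the concern to the p-value. But the SAP plans that p-value, gives it a column and sets a level for it.
- **The p-values are exploratory and no confirmatory testing is planned.** This also stands, and it limits severity. An exploratory p-value must still be reproducible from the plan, and the label does not say which test was run.
- **The illustration depends on a small shift.** A shift of 0.15 category is 0.15/1.5 = 0.10 to 0.15/1.2 = 0.125 SD. At 0.35, disagreement among the three boundaries falls to 17–25%, and at 0.50 it nearly vanishes. This is correct: the choice matters for a small shift and hardly at all for a moderate one. The documents do not say which to expect.
- **The row-by-row reading has the least support.** No text plans 12 tests, and the extracted table does not show how the P cells are laid out. The 35–37% figure applies only to that reading.
- **McNemar is often used loosely for Bowker's test, so naming Bowker and its table would be enough.** That would make the p-value reproducible. It would still leave an ordinal scale tested by a method that ignores order and is not aimed at improvement.

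One caveat: the SAP's numbering skips 5.2.6 and Tables 34 to 47, so the absence of a two-level PGE is established only for the text available. Section 5.2.7 and Table 24, where the definition belongs, contain none.

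**Conclusion.** The concern holds. As written, the test cannot be run on the PGE as the documents define it, and the Table 24 p-value cannot be reproduced from the SAP. That follows from the text alone and needs no assumption. How much it matters does depend on assumptions (correlation, SD, baseline mean and shift): at a shift of 0.15 to 0.25 category the unstated cut-point often decides significance, while at 0.50 it almost never does.

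This should be fixed, but its reach is limited to one exploratory p-value for a secondary endpoint.

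**What to change.** In SAP 5.2.7 and the Table 24 footnote, replace McNemar with one named paired ordinal test. Suggested wording:

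> *The change in PGE score (visit 2 minus visit 1, scores 1 to 8) will be tested with the Wilcoxon signed-rank test, and one p-value will be reported.*

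Alternatively, keep McNemar for a single dichotomy fixed before the data are analysed, for example scores 5–8 versus 1–4. If a test of the full square table is really intended, the least change is to name it and say whether it applies to the 8x8 or the 4x4 table. The signed-rank test suits the declared ordinal scale better.

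Optionally, add a visit 1 by visit 2 shift table of the four pooled categories, with the number and percentage improved, unchanged and worsened.

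The cost is one sentence and one footnote. The shift table uses data already collected.

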5.2.8. Handling of missing data

In context of PF-10 questionnaire, if less than half of the items on the PF-10 for a patient are missing, the missing values will be replaced with the mean of the other values and the PF-10 score will be calculated. If half or more of the items on the PF-10 are missing, no score will be calculated and the PF-10 score will be marked as not available.

No other missing data will be imputed. If patients have missing values for any other endpoints, these patients will be excluded from the analysis of that endpoint.

6. PLANNED ANALYSIS

6.1. STUDY POPULATION

6.1.1. Recruited and assessable patients

According to the section 5.2.2, three populations will be used for the analysis: All screened patients, Treated Set (TS) and Full Analysis Set (FAS). Details of patients excluded from the TS and patients excluded from the FAS will be included in Annex 2, section 8.2.

The important protocol violations will be described in the following table:

Table 1. Important protocol violations-All screened patients		
	n	%
Total patients		100.0
Total with violation of informed consent (IC-1)		
Total with violation of any other inclusion criterion		
Total with violation of any exclusion criterion		
Total with violation of any inclusion or exclusion criterion		

The inclusion criteria and exclusion criteria based on all screened patients according to CRFs:

Table 2. Inclusion and Exclusion criteria-All screened patients		
	n	%
Total patients at screen		
Inclusion criteria not fulfilled		
IC1. Written informed consent prior to participation		
IC2. Female and male patients ≥ 40 years of age		
IC3. Patients diagnosed with COPD and requiring dual bronchodilator (LAMA + LABA) treatment according to approved Spiolto® Respimat® SmPC and GOLD guideline recommendation		
Exclusion criteria fulfilled		
EC1. Patients with contraindications according to Spiolto® Respimat® SmPC		
EC2. Patients who have been treated with a LABA/LAMA combination (free and fixed dose) in the previous 6 months		
EC3. Patients continuing LABA/ICS treatment should not be additionally treated with Spiolto® Respimat® in order to avoid a double dosing of long-acting beta-agonists		
EC4. Patients for whom further follow-up is not possible at the enrolling site during the planned study period of approx. 6 weeks		
EC5. Pregnancy and lactation		
EC6. Patients currently listing for lung transplantation		

Table 2. Inclusion and Exclusion criteria-All screened patients		
	n	%
EC7. Current participation in any clinical trial or any other non-interventional study of a drug or device		

The disposition of patient will be described in the following table:

Table 3. Disposition of patients-All screened patients		
	n	%
Total patients at screen		
Total patients at visit 1		
Total patients at visit 2		
Total patients on Reason for not performing visit 2		
Adverse event		
Serious adverse event		
Patient's wish		
Withdrawn consent		
Lost to follow-up		
Patient died		
Other		
Total patients for discontinuation		
Lost to follow-up		
Not meet inclusion/exclusion criteria		
Adverse event		
Protocol deviation		
Patient's wish		
Investigator's wish		
Other		

The following table describes the number of assessable patients with data in visit 1 and visit 2 according the sample sets (screened patients, TS, FAS):

[figure not shown]
Table 4. Assessable patients by visit and sample set				
	Recruited patients n (%)	All screened patients n (%)	Assessable patients in TS n (%)	Assessable patients in FAS n (%)
Visit 1				
Visit 2				

All screened patients: All recruited patients with informed consent and date of registration.

Treated Set (TS): All screened patients with at least one documented administration of Spiolto® Respimat®.

Full Analysis Set (FAS): All screened patients with at least one documented administration of Spiolto® Respimat® and available PF-10 score at visit 1 and visit 2.

Figure 3. Flow chart of patients recruited onto the study

*In context of PF-10 questionnaire, if less than half of the items on the PF-10 for a patient are missing, the missing values will be replaced with the mean of the other values and the PF-10 score will be calculated. If half or more of the items on the PF-10 are missing, no score will be calculated and the PF-10 score will be marked as not available.

In the ANNEX 2. DETAILS OF THE NON-ASSESSABLE PATIENTS , the lists of the non-assessable patients in TS and FAS will be specified.

Table 5. Summary of analysis population and endpoints

n %	Baseline characteristics	Characteristics after 6 weeks	Primary endpoint	Secondary endpoints	Safety endpoints
Treated Set (TS)	X	X			X
Full Analysis Set (FAS)			X	X	

All screened patients: All recruited patients with informed consent and date of registration.

Treated Set (TS): All screened patients with at least one documented administration of Spiolto® Respimat®.

Full Analysis Set (FAS): All screened patients with at least one documented administration of Spiolto® Respimat® and available PF-10 score at visit 1 and visit 2.

6.2. DESCRIPTION OF THE SAMPLE AT BASELINE VISIT (VISIT 1, TS)

This section will describe the socio-demographic characteristics, anthropometric data, smoking history and baseline characteristics in terms of the COPD diagnosis, exacerbations, lung function, concomitant diseases, concomitant medication, and previous and current treatment for COPD of the **Treated Set (TS)** (n=xxx) (see *Table 4*).

6.2.1. Bio-demographic characteristics

This section will describe the socio-demographic data and anthropometric data of the treated patients being studied.

Table 6. Socio-demographic data - Treated Set (TS)

	Total
Age (years)	
Mean (SD)	
95% CI	
Median (P25; P75)	
(Min; Max)	
N	
Pooled age n (%)	
< 65 years	
≥ 65 years	
Gender n (%)	
Male	
Female	
Employment status n (%)	
Working	
Unemployed	
Temporarily unable to work	
Permanently unable to work	
Retired	
Other ¹	

¹Specify 'other':

Table 7. Anthropometric data - Treated Set (TS)

	n	mean	SD	(95% CI)	Median [P25 ; P75]	Min	Max	p ¹
Weight (kg)								
Male								
Female								
Height (cm)								
Male								
Female								
BMI (kg/m²)								

Table 7. Anthropometric data - Treated Set (TS)								
	n	mean	SD	(95% CI)	Median [P25 ; P75]	Min	Max	p¹
Male								
Female								

¹ Student's t-test/Mann-Whitney U test

6.2.2. Smoking history

This section will describe the smoking history of the assessable patients being studied.

Table 8. Smoking history - Treated Set (TS)		Total
Smoking n (%)		
Non-smoker		
Ex-smoker		
Smoker		
Number of pack-years - Ex-smoker		
Mean (SD)		
95% CI		
Median (P25; P75)		
(Min; Max)		
N		
Number of pack-years - Smoker		
Mean (SD)		
95% CI		
Median (P25; P75)		
(Min; Max)		
N		
Number of pack-years¹		
Mean (SD)		
95% CI		
Median (P25; P75)		
(Min; Max)		
N		

¹ Sample of ex-smokers and smokers (n=xx)

Pack-years = (number of cigarettes smoked per day x number of smoking years) / 20

6.2.3. Start of COPD

This section will describe the time from the diagnosis of COPD to the baseline visit (visit 1).

Table 9. Medical history - Treated Set (TS)	
	Total
Time from COPD diagnosis to date of baseline visit (years)	
Mean (SD)	
95% CI	
Median (P25; P75)	
(Min; Max)	
N	

6.2.4. Exacerbations

This section will describe the exacerbation episodes, attendance at the emergency department and hospital admission which have occurred in the last 12 months relative to the baseline visit (visit 1).

Table 10. Exacerbations in the last 12 months - Treated Set (TS)	
	Total
Has the patient experienced any moderate COPD exacerbation episodes (which required corticosteroids and/or systemic antibiotics)? n (%)	
Yes	
No	
Unknown	
Number of moderate exacerbation episodes¹	
Mean (SD)	
95% CI	
Median (P25; P75)	
(Min; Max)	
N	
Frequency of moderate exacerbation episodes¹ n (%)	
0	
1	
2	
...	
Frequency of moderate exacerbation episodes¹ n (%)	
≤ 1 exacerbation episode	
≥ 2 exacerbation episodes	
Time from the last episode until visit 1 (months)¹	
Mean (SD)	
95% CI	
Median (P25; P75)	
(Min; Max)	
N	

Table 10. Exacerbations in the last 12 months - Treated Set (TS)

	Total
Did the patient come to the emergency department because of COPD (exacerbation)? n (%)	
Yes	
No	
Unknown	
He/she came to the emergency department in the Primary setting² n (%)	
He/she came to the emergency department in the Hospital setting² n (%)	
Number of times he/she came to the emergency department in the Primary setting³	
Mean (SD)	
95% CI	
Median (P25; P75)	
(Min; Max)	
N	
Number of times he/she came to the emergency department in the Hospital setting⁴	
Mean (SD)	
95% CI	
Median (P25; P75)	
(Min; Max)	
N	
Did he/she require hospital admission because of his/her COPD (severe exacerbation)? n (%)	
Yes	
No	
Unknown	
Number of hospitalisations that he/she has had⁵	
Mean (SD)	
95% CI	
Median (P25; P75)	
(Min; Max)	
N	
Total number of days admitted⁵	
Mean (SD)	
95% CI	
Median (P25; P75)	
(Min; Max)	
N	
Time from the last hospitalisation until visit 1 (months)⁵	
Mean (SD)	
95% CI	

Table 10. Exacerbations in the last 12 months - Treated Set (TS)

	Total
Median (P25; P75)	
(Min; Max)	
N	

¹ If the patient has experienced any moderate exacerbation episodes (n=xx)

² If the patient came to the emergency department because of his/her COPD (n=xx)

³ If the patient came to the emergency department in the Primary setting (n=xx)

⁴ If the patient came to the emergency department in the hospital setting (n=xx)

⁵ If the patient required hospital admission because of his/her COPD (n=xx)

